The lungs are known to be colonised with different strains of bacteria [[Erb-Downward](#), 2011]. In COPD patients, acquisition of new bacterial strains is believed to be an important cause of AECOPD [[Sethi](#), 2002]. Although estimates vary widely, Non-typeable *Haemophilus influenzae* (NTHi) appears to be the main bacterial pathogen associated with AECOPD (11-38%), followed by *Moraxella catarrhalis* (*M. catarrhalis*) (3-25%) and *Streptococcus pneumoniae* (*S. pneumoniae*) (4-9%) [[Alamoudi](#), 2007; [Bandi](#), 2003; [Hutchinson](#), 2007; [Ko](#), 2007; [Larsen](#), 2009; [Murphy](#), 2005; [Papi](#), 2006; [Sethi](#), 2002; [Sethi](#), 2008].

Reducing the frequency and severity of AECOPD is one of the main goals of COPD maintenance treatment. The severity of AECOPD can be graded according to the intensity of medical intervention required (see [Table 2](#)) [[Wedzicha, 2007](#)].

Table 2 Classification of severity of AECOPD

Grade	Intensity of medical intervention
Mild	Can be controlled with an increase in dosage of regular medications
Moderate	Requires treatment with systemic corticosteroids and/ or antibiotics
Severe	Requires hospitalisation

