- Chronic use of antibiotics for prevention of AECOPD (*e.g.* azithromycin).
- Receiving oxygen therapy.
- Planned lung transplantation.
- Planned/ underwent lung resection surgery (*e.g.* lung volume reduction surgery or lobectomy).
- Diagnosis of α -1 antitrypsin deficiency as the underlying cause of COPD.
- Diagnosed with a respiratory disorder other than COPD (such as sarcoidosis, active tuberculosis, clinically significant bronchiectasis, lung fibrosis, pulmonary embolism, pneumothorax, current diagnosis of asthma in the opinion of the investigator), or chest X-ray/ CT scan revealing evidence of clinically significant abnormalities not believed to be due to the presence of COPD. Subjects with allergic

rhinitis do not need to be excluded and may be enrolled at the discretion of the investigator.

- History of any reaction or hypersensitivity likely to be exacerbated by any component of the vaccines and/ or the bronchodilator used for spirometry assessment during the study.
- Contraindication for spirometry testing (such as recent eye surgery, recent thoracic or abdominal surgery procedures, unstable cardiovascular status, recent myocardial infection or pulmonary embolism).
- Clinically significant* abnormality in haematology (haemoglobin, platelets or WBC) or biochemistry parameter (ALT, AST or creatinine), as per the judgement of the investigator.

* As the study participants are COPD patients, various pre-existing haematological/biochemical abnormalities might be detected. The investigator should use his/ her clinical judgement to decide which ones are clinically significant.

- Acute cardiac insufficiency.
- Malignancies within the previous 5 years (excluding non-melanotic skin cancer and carcinoma *in situ* of the cervix, if considered cured) or lymphoproliferative disorder.
- Any known disease or condition likely to cause death during the study period.
- Acute disease and/ or fever at the time of Screening.
 - Fever is defined as oral or axillary temperature $\geq 37.5^{\circ}\text{C}$. The preferred route for recording temperature in this study will be oral.
 - Subjects with acute disease and/ or fever at the time of Screening may be enrolled at a later date if enrolment is still open. Subjects with a minor illness without fever may be enrolled at the discretion of the investigator.
- Pregnant or lactating female.
- Current alcoholism and/ or drug abuse.

Refer to the [glossary of terms](#) for the definition of alcoholism.

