7.6.1. Recording of concomitant medications/products and concomitant vaccination

All vaccinations and medications (except for vitamins and dietary supplements) administered throughout the study period (including dose, unit, frequency and reason for use) must be recorded in the eCRF.

7.6.2. Concomitant medications/products and vaccines that may lead to the elimination of a subject from ATP analysis for immunogenicity

The use of the following concomitant medications/products/vaccines will not require withdrawal of the subject from the study but may determine a subject's evaluability in the ATP analysis for *immunogenicity*.

- Any investigational or non-registered product (drug or vaccine) other than the study vaccine used at any time during the entire study period.
- A vaccine not foreseen by the study protocol administered during the period starting 30 days before and ending 30 days after each dose of vaccine*, with the exception of any influenza or pneumococcal vaccines which may be administered \geq 15 days preceding or following any dose of study vaccine.

* In case an emergency mass vaccination for an unforeseen public health threat (e.g. a pandemic) is organised by the public health authorities, outside the routine immunisation program, the time period described above can be reduced if necessary

for that vaccine provided it is licensed and used according to its summary of product characteristics (SmPC) or prescribing information (PI) and according to the local governmental recommendations and provided a written approval of the Sponsor is obtained.

- Immunoglobulins or any blood products administered at any time during the study period.
- Immunosuppressants or other immune-modifying drugs administered chronically (*i.e.* more than 14 days) at any time during the study period (*e.g.* methotrexate). Use of corticosteroids is allowed as per local treatment recommendations.

7.6.3. Concomitant medications/ products that may lead to the elimination of a subject from the ATP analysis for efficacy

In addition to the concomitant medications/ products/ vaccines described in the Section 7.6.2, the use of the following medications/ products will not require withdrawal of the subject from the study but may determine a subject's evaluability in the ATP analysis for *efficacy*.

- Underwent lung transplantation/ lung resection surgery at any time during the entire study period.
- Chronic use of antibiotics at any time during the entire study period.

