11.10. Analysis of impact of the investigational vaccine on AECOPD

The analysis will be performed on the ATP cohort for efficacy. If the percentage of vaccinated subjects excluded from the ATP cohort for efficacy is more than 10%, a second analysis based on the TVC will be performed to complement the first analysis.

The following incidence rates will be computed over a period starting 1 month post-Dose 2 and lasting for 1 year, with 95%CI:

- NTHi-associated moderate and severe AECOPD.
- NTHi-associated all-severity AECOPD.
- All-cause moderate and severe AECOPD.
- All-cause, all-severity AECOPD.

The 95% CI of the incidence rate will be computed using a model which accounts for repeated events. The Generalised linear model assuming the Negative Binomial distribution for the response variable with logarithm as link function, and the logarithm of time for follow-up as an offset variable will be used. If the model does not converge, the Poisson distribution will be used instead of the Negative Binomial one.

Vaccine efficacy (VE) for AECOPD events will be defined as:

$$VE(AECOPD) = 1 - R_{vaccine} / R_{control}$$

with:

- $R_{vaccine}$ = average yearly incidence rate of AECOPD events per subject in the group 10-AS01E.
- $R_{control}$ = average yearly incidence rate of AECOPD events per subject in the Control group.

In case the 95% CI of the VE cannot be estimated, *e.g.* when no event is observed in the group 10-AS01E (leading to a VE of 100%), then an exact procedure will be used to estimate a VE and its 95% CI. This exact procedure will be based on the number of subjects with event instead of on the average number of event per subject in each group.

VE in the prevention of NTHi-associated moderate and severe AECOPD and its 95% CI will be calculated.

VE in the prevention of NTHi-associated all-severity AECOPD, of all-cause moderate and severe AECOPD and of all-cause, all-severity AECOPD and their 95% CI will also be calculated.

The time until first AECOPD as of 1 month post-Dose 2 will be computed with exact 95% CI by group. Subjects who exacerbate before 1 month post-Dose 2 will not be taken into account in this analysis.

The proportion of sputum samples with exact 95% CI obtained at each visit (scheduled visits and AECOPD-driven visits) and positive for bacterial pathogens (overall and by bacterial pathogen) will be computed by group and overall. The exact 95% CI will be estimated assuming independence of bacterial results across sputum samples.

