5.4. ATP cohort for analysis of efficacy

The ATP cohort for analysis of efficacy will include all subjects in the TVC:

- Who met all eligibility criteria.
- For whom the administration route and site of the vaccines was according to protocol.
- Who complied with the vaccination schedule
- Who received the study vaccine according to protocol procedures.
- Not having received a medication/ product/ vaccine that may lead to elimination from the ATP analysis for efficacy.

The list of applicable elimination codes for each cohort can be found in the study specific form FORM-BIO-CLIN-9004-05 Criteria for eliminating subjects from the analyses.

Cohort	Elimination codes	Eli Type
ATP cohort for analysis of immunogenicity	1010-2500	MA

Statistical Analysis Plan

Study alias & e-track number(s): NTHi-004 (200157)

ATP cohort for analysis of efficacy	1010-2500	EF
ATP cohort for analysis of persistence of immunogenicity	1010-2500	FU

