6.1.3. Analysis of impact of the investigational vaccine on AECOPD incidence

The analysis will be performed on the ATP cohort for efficacy. If the percentage of vaccinated subjects excluded from the ATP cohort for efficacy is more than 10%, a second analysis based on the TVC will be performed to complement the first analysis.

The following incidence rates will be computed over a period starting 1 month post-Dose 2 and lasting for 1 year, with 95%CI:

- NTHi-associated moderate and severe AECOPD. (See definition in section 7.1.4)
- NTHi-associated all-severity AECOPD.
- All-cause moderate and severe AECOPD.
- All-cause, all-severity AECOPD.

Vaccine efficacy (VE) for AECOPD events will be defined as:

$$VE (AECOPD) = 1 - R_{vaccine} / R_{control}$$

with:

- $R_{vaccine}$ = average yearly incidence rate of AECOPD events per subject in the group 10-AS01E.
- $R_{control}$ = average yearly incidence rate of AECOPD events per subject in the Control group.

In case the 95% CI of the VE cannot be estimated, *e.g.* when no event is observed in the group 10-AS01E (leading to a VE of 100%), then an exact procedure will be used to estimate a VE and its 95% CI. This exact procedure will be based on the number of subjects with event instead of on the average number of event per subject in each group.

Statistical Analysis Plan

Study alias & e-track number(s): NTHi-004 (200157)

VE in the prevention of NTHi-associated moderate and severe AECOPD and its 95% CI will be calculated.

VE in the prevention of NTHi-associated all-severity AECOPD, of all-cause moderate and severe AECOPD and of all-cause, all-severity AECOPD and their 95% CI will also be calculated.

The 95%CI of the incidence rate will be computed using a model which accounts for repeated events. The Generalised linear model assuming the Negative Binomial distribution for the response variable with logarithm as link function, and the logarithm of time for follow-up as an offset variable will be used. In addition, the following covariates (as per randomization) will be taken into account:

- country,
- number of moderate/severe exacerbations reported in the 12 months prior to enrolment,
- COPD status at enrolment (derived by GSK from the Visit 1 spirometry results)
- Age (below or equal to median/above median)

If the model does not converge, the Poisson distribution will be used instead of the Negative Binomial one.

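### AECOPD efficacy is estimated on an ATP cohort whose exclusions can follow from exacerbations, and a total vaccinated cohort estimate is planned only if more than 10% are excluded

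*SAP*

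**What the plan says.** **Analysis set.** For AECOPD incidence and VE, Protocol 11.10 states: "The analysis will be performed on the ATP cohort for efficacy". It continues: "If the percentage of vaccinated subjects excluded from the ATP cohort for efficacy is more than 10%, a second analysis based on the TVC" is run to complement the first. SAP Amendment 1 section 6.1.3 has the same rule: the TVC is added if the share excluded "is more than 10%, a second analysis based on the TVC will be performed to complement the first analysis". This covers NTHi-associated and all-cause AECOPD, each as moderate/severe and as any severity. No other TVC analysis of these rates or of VE is planned.

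**Who leaves the cohort.** SAP 5.4 requires, among other things, "Not having received a medication/ product/ vaccine that may lead to elimination from the ATP analysis for efficacy". Protocol 7.6.3 lists "Chronic use of antibiotics at any time during the entire study period", along with lung transplantation or resection and the products in 7.6.2. The wording is permissive: such use may affect evaluability. Section 7.6.2 defines chronic use as more than 14 days for immunosuppressants; no definition is given for antibiotics.

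**Links to the outcome.** Table 2 of the Protocol defines a moderate AECOPD as one that "Requires treatment with systemic corticosteroids and/ or antibiotics". Protocol 5.3 bars enrolment for "Chronic use of antibiotics for prevention of AECOPD". Protocol 7.5 makes a moderate or severe AECOPD that is ongoing, or resolved for less than 7 days, a reason to postpone vaccination. Table 9 allows 60 to 75 days from Visit 1 to Dose 2, and Protocol 11.5.4 makes compliance with that schedule an ATP criterion.

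**Elsewhere in the plan.** Safety and the quality-of-life, lung-function and exercise analyses use the TVC first (SAP 6.1.1, 6.1.5). Biomarkers use ATP first, but add the TVC at 10% or more, not above 10% (SAP 6.1.6).

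**The concern.** An exclusion decided after randomisation is harmless to a comparison only if it is unrelated to outcome and treatment. Here it may be related to both. The Protocol itself names long-term antibiotics as a means of preventing exacerbations. Since subjects already taking them for that purpose cannot enrol, someone caught by 7.6.3 on that ground should have started during the study, plausibly because exacerbations kept occurring. The subject is then dropped whole, including events and follow-up before the antibiotic.

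The Dose 2 route works similarly. Those exacerbations precede the counting period, which starts one month after Dose 2, so the link is through the subject's tendency to exacerbate and not through counted events.

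The 10% condition is a weak safeguard. It counts subjects, whereas the rate depends on events, and frequent exacerbators carry more than their share. It also pools the arms, so a lopsided set of exclusions can stay below it. In that case VE would be reported from the selected cohort with no TVC estimate beside it.

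**Working it through.** **The plan's own figure.** The only sample-size statement (Protocol 11.4) concerns adverse events with 70 per group: more than 50% chance of seeing one at 1% incidence and more than 97% at 5%. Check: 1 − 0.99^70 = 50.5%; 1 − 0.95^70 = 97.2%. Both reproduce. There is no sizing for efficacy and no AECOPD rate, dispersion or expected VE, so every rate below is an assumption.

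**Where the trigger falls.** About 140 subjects, 1:1 (Protocol 6.2.2.2.1). 14/140 = 10.0%, not more than 10%, so no TVC analysis; 15/140 = 10.7%, so it runs. If 14 excluded subjects exacerbate at r times the overall mean, they hold 14r/140 of the events: 20% at r = 2, 30% at r = 3.

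**Worked example (assumed).** Seven controls and three vaccinees have 3 AECOPD per year; the others have 1.0 (control) and 0.8 (vaccine).
- Control, all: (63×1 + 7×3)/70 = 84/70 = 1.20.
- Vaccine, all: (67×0.8 + 3×3)/70 = 62.6/70 = 0.894.
- VE, all: 1 − 0.894/1.20 = 25.5%. VE, ATP: 1 − 0.8/1.0 = 20%.
- Excluded: 10/140 = 7.1%, so no TVC analysis.

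**Effect of the split between arms.** Exclude kv vaccinees and kc controls (kv + kc = 14), each at r times their own arm's mean. The remaining mean in an arm is m(70 − kr)/(70 − k). With true VE 30%,

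ATP VE = 1 − 0.7 × [(70 − kv·r)/(70 − kv)] / [(70 − kc·r)/(70 − kc)].

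For 4/10 at r = 2: 1 − 0.7 × (62/66)/(50/60) = 21.1%.

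| Vaccine/control excluded | r = 1.5 | r = 2 | r = 3 |
|---|---|---|---|
| 7/7 | 30.0% | 30.0% | 30.0% |
| 9/5 | 32.6% | 35.4% | 41.7% |
| 5/9 | 27.3% | 24.2% | 16.0% |
| 4/10 | 26.0% | 21.1% | 7.7% |
| 14/0 | 38.8% | 47.5% | 65.0% |
| 0/14 | 20.0% | 6.7% | −40.0% |

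If each of the 14 is equally likely to come from either arm, a split at least as uneven as 9/5 in either direction has probability 2×(1+14+91+364+1001+2002)/2^14 = 6946/16384 = 42%. For 10/4 or worse it is 2×1471/16384 = 18%. For 14/0 or 0/14 it is 2/16384, about 0.01%, so the last two rows are bounds, not expectations.

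**Removal driven by event count (simulation).** Counts are gamma-Poisson, with control rate 1, 1.5 or 2 per year and dispersion 0.5 or 1. Subjects with 3 or more events are removed with probability 0.3 or 0.5, or those with 4 or more with probability 0.5.

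| True VE | Mean ATP VE over scenarios |
|---|---|
| 0 | about 0 |
| 30% | about 26% to 29% |
| 50% | about 44% to 48% |

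The probability of 14 or fewer exclusions, hence no TVC analysis, is 0.75 or more in 43 of the 54 scenarios and 0.04 to 0.67 in the 11 others, which have the heavier removal. Only removals of this one kind are simulated; other ATP exclusions count toward the trigger and would lower that probability.

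**The case against.** The case for leaving the plan alone has several sound parts.

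- **Status.** AECOPD impact is a tertiary objective to explore (Protocol 2.3), and between-group efficacy comparisons are descriptive and to be read with caution (11.13). Safety, the primary objective, is analysed on the TVC. This stands, and it limits how much rests on the point.
- **Certainty of removal.** A reader might infer that every subject given repeated antibiotics is dropped. The documents do not support that. Section 7.6.3 is permissive, chronic use of antibiotics is undefined, and nothing says that ordinary treatment of an exacerbation counts. The applied criteria are in a separate elimination form that is not among the documents. That exacerbations lead to chronic use is an inference from the Protocol's reference to prophylaxis.
- **Direction.** A reader might also infer that the rule favours the vaccine. Event-driven removal does the opposite: it takes out more controls when the vaccine works, pulls VE toward zero, and creates no expected efficacy where there is none. Inflation needs an excess of excluded vaccinees, by chance or for another reason.
- **Size against noise.** In the worked example (84 against 62.6 events, one year each), the 95% CI for VE in all subjects is about −3% to 46% (Poisson), or −11% to 50% (negative binomial, assumed dispersion 0.5). A shift of five or six points is small beside that.
- **Other exclusions.** The trigger pools every reason for leaving ATP. Exclusions unrelated to exacerbation rate add no bias of this kind and bring the TVC analysis closer.
- **Other tables.** ATP exclusion counts are tabulated, and healthcare use for AECOPD is summarised on the TVC. Neither gives a TVC estimate of VE, and no tabulation of ATP exclusions by reason is specified.

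These points reduce the weight of the concern. None gives a reason to make the TVC analysis conditional.

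**Conclusion.** The point holds as a modest, inexpensive improvement. The AECOPD rates and VE come from a cohort that may lose subjects because of events related to the outcome. Up to 14 of 140 could be lost, possibly unequally by arm, without a planned TVC estimate.

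Under the assumed rates, event-driven removal costs about 1 to 6 points of VE, toward zero. Chance imbalance can move a 30% VE further: to 21% or 35% for splits of 4/10 or 9/5 at twice the mean rate, and more at three times. These sizes assume that all 14 excluded subjects are frequent exacerbators, which the documents neither state nor rule out.

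It would go too far to say that the plan builds in a bias favouring the vaccine, that removal is automatic, or that the trial's main conclusion is affected.

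**What to change.** In SAP 6.1.3 and Protocol 11.10, delete the 10% condition. State that the TVC analysis of all four AECOPD rates and VE is always run and reported beside the ATP analysis. Add a table of exclusions from the ATP efficacy cohort by arm and reason. Because the counting period is defined from Dose 2, the sentence should also say how follow-up starts for TVC subjects who never received it. The TVC efficacy analysis is limited to subjects with efficacy data (SAP 5.1), so it should be labelled accordingly.

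Censoring ATP follow-up at the start of chronic antibiotics is not a good substitute. Follow-up would stop because of earlier exacerbations, so the censoring would itself be informative, and the start date cannot be derived while chronic use is undefined.

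The cost is one more run of existing programs, a second set of tables and a few lines of wording.

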3. STUDY DESIGN OVERVIEW

Protocol waivers or exemptions are not allowed with the exception of immediate safety concerns. Therefore, adherence to the study design requirements, including those specified in the outline of study procedures (Section 6.5), are essential and required for study conduct.

Figure 1 Study design overview

Scr = Screening; **V** = Visit; **D** = Day; **random** = randomisation; **VACC** = vaccination; **BS(1)** = blood sample for safety; **BS(2)** = blood sample for humoral immunogenicity; **BS(3)** = blood sample for cell-mediated immunity (CMI); **BS(4)** = blood sample for biomarkers; **SP** = sputum sample

In addition to the scheduled study visits depicted above, *ad hoc* AECOPD-driven study visit(s) and/or phone contact(s) will take place for each AECOPD occurring from first vaccination up to study conclusion. An AECOPD visit will be scheduled as soon as possible after the onset of AECOPD symptoms (maximum 96 hours after and, if applicable, preferably before starting treatment with antibiotics). In addition, follow-up phone call(s) and/or visit(s) will take place to determine the end of the AECOPD. These contacts will take place at least every 2 weeks, until the AECOPD has resolved.

- **Experimental design:** Phase II randomised, observer-blind, placebo-controlled, multi-centre study with 2 parallel groups.
- **Duration of the study:** for each subject enrolled, the study will last approximately 16 months from Visit 1 up to study end:
 - **Epoch 001:** starting at Screening and ending at study conclusion.
- **Study groups:**
 - **Group 10-AS01E:** approximately 70 subjects receiving 2 doses of the investigational NTHi vaccine.
 - **Group Control:** approximately 70 subjects receiving 2 doses of placebo.

Table 3 Study groups and epoch foreseen in the study

Study groups	Number of subjects	Age (Min/Max)	Epoch
			Epoch 001
10-AS01E	~70	40 - 80 years	X
Control	~70	40 - 80 years	X

- **Control:** placebo control.
- **Vaccination schedule:** 0, 2 months (*i.e.* at Visit 1 [Day 0] and Visit 4 [Day 60]).

Table 4 Study groups and treatments foreseen in the study

Treatment name	Vaccine/ product name	Study groups	
		10-AS01E	Control
10µgAg/ AS01E	NTHI-10	X	
	AS01E		
Placebo	NaCl		X

- **Treatment allocation:** subjects will be minimised by:
 - Age (40 - 59 years or 60 - 80 years).
 - Number of moderate/ severe AECOPD in the previous year (< 2 or \geq 2).
 - GOLD grade (GOLD 2 or GOLD 3).

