6.2.2.2. Treatment allocation to the subject

The treatment numbers will be allocated by dose.

6.2.2.2.1. *Study group and treatment number allocation*

The target will be to enrol approximately 140 eligible subjects who will be randomly assigned to the 2 study groups in a (1:1) ratio (approximately 70 subjects in each group).

Allocation of a subject to a study group at the investigator site will be performed using a centralised randomisation system on the internet (SBIR). The randomisation algorithm will use a minimisation procedure accounting for age (40 - 59 years or 60 - 80 years), number of moderate/ severe AECOPD in the previous year (< 2 or \geq 2) and GOLD grade (GOLD 2 or GOLD 3). All factors will have equal weight in the minimisation algorithm.

At Visit 1, before administration of vaccine Dose 1 to eligible subjects who signed and dated the ICF at the Screening Visit, the dedicated site staff will access SBIR. Upon providing the subject's age category (40 - 59 years or 60 - 80 years), number of moderate/ severe AECOPD in the previous year and his/ her GOLD grade, the randomisation system will determine the study group and will provide the treatment number to be used for the first dose.

The number of each administered treatment must be recorded in the eCRF on the Vaccine Administration screen.

When SBIR is not available, refer to the SBIR user guide or the SPM for specific instructions.

6.2.2.2.2. *Treatment number allocation for subsequent doses*

For each dose subsequent to the first dose, the dedicated study staff will access SBIR. Upon providing the subject identification number, the system will provide a treatment number consistent with the allocated study group.

The number of each administered treatment must be recorded in the eCRF on the Vaccine Administration screen.

When SBIR is not available, refer to the SBIR user guide or the SPM for specific instructions.

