6.5. Outline of study procedures

6.5.1. Lists of study procedures during scheduled study visits

Table 7 List of study procedures during scheduled study visits

Epoch	Type of contact	Epoch 001									
		Screening ^(a b)	Visit 1	Visit 2	Visit 3	Visit 4	Visit 5	Visit 6	Visit 7	Visit 8	Visit 10
Timepoint	pre-D0	D0	D7	D30	D60	D67	D90	D180	D270	D360	D450
Sampling timepoint	Screening	Pre-Vacc	Post-Vac 1	Pre-Vacc 2	Post-Vacc 2						
Informed consent	●										
Check inclusion/exclusion criteria	● ^(b)	○									
Record history of moderate and severe AECOPD within the previous year	○	●									
Check subject's COPD status		●	●	●	●	●	●	●	●	●	●
Record demographic data	●										
Record medical history, including significant comorbidities	○	●									
Vaccination history	○	●									
Smoking exposure history	X										
Smoking status	●								●		●
Physical examination	● ^(b)	○	○	○	○	○	○	○	○	○	○
Measure/ record height and weight	●								○		●
Pre- and post-bronchodilator spirometry	X								X		X
Chest X-ray ^(c)	●										
Urine pregnancy test ^(d)	● ^(b)	●			●						
Blood sampling:											
For safety assessment (~5.5 mL)	● ^(b)	●	●	●	●	●	●	●	●	●	●
For humoral immunogenicity (~25.5 mL)		●		●	●	●	●	●	●	●	●
For CMI (~40 mL) ^(e)		●					●		●		●
For biomarkers (~12.8 mL)		●									●
Sputum sampling ^(f)	●							●	●	●	●
Check contraindications to vaccination		○			○ ^(g)						
Record pre-vaccination body temperature		●			●						
Treatment number allocation ^(h)		●			●						
Vaccination		●			●						
Distribute paper Diary Card for recording of vaccine reactogenicity		○	○		○	○					
Return paper Diary Card for recording of vaccine reactogenicity			○	○		○	○				

CONFIDENTIAL

200157 (NTHI-004)
Protocol Amendment 3 Final

Epoch	Epoch 001										
Type of contact	Screening ^(a b)	Visit 1	Visit 2	Visit 3	Visit 4	Visit 5	Visit 6	Visit 7	Visit 8	Visit 9	Visit 10
Timepoint	pre-D0	D0	D7	D30	D60	D67	D90	D180	D270	D360	D450
Sampling timepoint	Screening	Pre-Vacc	Post-Vac 1	Pre-Vacc 2	Post-Vacc 2						
Transcription of paper Diary Card for recording of vaccine reactogenicity			●	●		●	●				
Record AEs		●	●	●	●	●	●	●	●	●	●
Report SAEs	● ^(b)	●	●	●	●	●	●	●	●	●	●
Report pregnancies		●	●	●	●	●	●	●	●		
Distribute paper Diary Card for recording of medication	O										
Record concomitant medications/products and vaccinations	O	●	●	●	●	●	●	●	●	●	●
Return paper Diary Card for recording of medication											O

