The frequency of all these AECOPDs will be presented. The estimated incidence rate with 95%CI of AECOPDs in which Hi (resp. Mcat, Sp) is present in culture and was not present in the previous visit estimated by a Generalised linear model assuming the Negative Binomial distribution will be estimated.

Time to first AECOPD event by baseline status - Cox regression model

The Cox's regression model including the risk factors:

- country,
- number of moderate/severe exacerbations reported in the 12 months prior to enrolment,
- COPD status at enrolment (derived by GSK from the Visit 1 spirometry results)
- Age (below or equal to median/above median)

as covariates (as per randomization) will be performed to model the time until the first occurrence of AECOPD episodes. Additional stratification/risk factor may be defined during the analyses like sex factor as exploratory analysis.

Statistical Analysis Plan

Study alias & e-track number(s): NTHi-004 (200157)

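### The AECOPD models present their covariates as those of the randomisation, but the age cut, country and the spirometry visit do not match the minimisation, and the history coding is left unstated

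*SAP*

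**What the plan says.** Protocol sections 3 and 6.2.2.2 describe a "minimisation procedure accounting for age (40 - 59 years or 60 - 80 years), number of moderate/ severe AECOPD in the previous year". The history factor has two levels, <2 and ≥2, and GOLD grade (2 or 3) is the third factor. All three have equal weight. Section 3 states the age factor as "Age (40 - 59 years or 60 - 80 years").

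SAP Amendment 1, section 6.1.3, introduces the covariates of the negative binomial model with "In addition, the following covariates (as per randomization) will be taken into account". Besides country, it lists:

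- for exacerbation history, "number of moderate/severe exacerbations reported in the 12 months prior to enrolment", without giving any levels;
- for lung function, "COPD status at enrolment (derived by GSK from the Visit 1 spirometry results"), a source discussed below;
- for age, a split written as "Age (below or equal to median/above median").

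The Cox model in the same section repeats the four items "as covariates (as per randomization) will be performed to model the time until the first occurrence of AECOPD episodes". SAP version 1 (section 6.2.4) has the same list.

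The GMC ANCOVA in SAP section 6.1.2 is coded differently. It uses the two protocol age bands, history as <2 or ≥2 and GOLD 2 or 3, and it names country without tying it to the randomisation. Protocol section 11.10 gives no covariates for the AECOPD model.

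**The concern.** The label and the list cannot both be followed. A programmer who follows the label fits age cut at 60; one who follows the list fits age cut at the median. The SAP does not say which cohort supplies that median. The analysis uses the ATP efficacy cohort and may be repeated on the TVC, so the cut could differ between the two.

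The source named for COPD status does not exist under the visit schedule. The history term could be fitted as a count or as two levels from the same sentence.

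At stake is whether the adjusted AECOPD estimates account for the factors balanced at allocation, and whether two statisticians would fit the same model. Under SAP section 8.1 the project statistician is unblinded at the Day 90 step and AECOPD analyses run in parallel with it, so open coding choices are better closed in writing beforehand.

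**Working it through.** The plan gives no figure on this point to reproduce. The main check sets the texts side by side.

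| Item | Minimisation (Protocol 3, 6.2.2.2, 6.6.3) | AECOPD models (SAP 6.1.3) | GMC ANCOVA (SAP 6.1.2) | Finding |
|---|---|---|---|---|
| Age | 40-59 / 60-80 | at or below / above median | 40-59 / 60-80 | different cut |
| Country | not a factor | listed under the label | listed, no label | wrong label |
| Lung function | GOLD 2 / 3 | COPD status from Visit 1 spirometry | GOLD 2 / 3 | wrong visit |
| History | <2 / ≥2; the Visit 1 total is entered in SBIR | number, no levels | <2 / ≥2 | coding unstated |

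**Spirometry.** In Protocol Table 7 the row "Pre- and post-bronchodilator spirometry" is marked at Screening and two later visits. Section 3 names these as Screening, Visit 8 and Visit 10. The only value before vaccination is therefore the Screening one.

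**Age: how many subjects change level.** With ages in whole years, the minimisation puts a subject in the upper level if age ≥ 60, and the SAP does so if age > m, where m is the sample median.

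- m = 59: age > 59 is the same as age ≥ 60, so nobody changes level.
- m ≥ 60: subjects aged 60 to m change level.
- m < 59: subjects above m and up to 59 change level.

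The documents give no age distribution. The following assumes ages normal, truncated to 40-80 and floored to whole years, with 140 subjects. Samples are grouped by their observed median, and entries are the mean number changing level.

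| Median | SD 9 | SD 8 | SD 7 |
|---|---|---|---|
| 59 | 0 | 0 | 0 |
| 60 | 7.5 | 8.2 | 9.1 |
| 62 | 19.9 | 22.1 | 24.5 |
| 65 | 37.3 | 40.7 | 44.9 |
| 68 | 52.1 | 55.7 | 59.7 |

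Hand check at median 65, SD 8, with the underlying mean at 65.5: [Φ((66−65.5)/8) − Φ((60−65.5)/8)] / [Φ((81−65.5)/8) − Φ((40−65.5)/8)] = 0.2790/0.9729 = 0.287, and 0.287 × 140 ≈ 40. Below the cut the pattern is the same: at a median of 58, about 6 to 8 subjects change level.

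**Effect on the model, as illustration.** All inputs here are assumed:

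- 140 subjects, one year of follow-up, no true vaccine effect, minimisation on the three protocol factors
- event rate 0.3 or 2 per year, dispersion 0.5 or 1
- age mean 65, SD 8; history 1 + Poisson(0.7); 45% GOLD 3; four countries without effect
- covariate effects either at the protocol cuts or log-linear in age and number of events

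This gives 16 scenarios of 300 trials each. Replacing the age cut at 60 by the median, with history kept at <2/≥2, moved the VE estimate by a median of 0.7 to 2.1 percentage points (95th percentile 3.6 to 10.5). The standard error of the log rate ratio changed by a factor of 1.000 to 1.011. The median width of the 95% CI for VE was 66 to 149 points, so the typical shift was about 1% to 2% of that width. These are orders of magnitude only. The Cox model was not simulated.

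**The case against.** Much can be said for leaving the text alone. The median split is pre-specified and uses neither treatment nor outcome. All three minimisation factors appear in some form. Adjusting for country is legitimate, and the ANCOVA does it too. Only one spirometry precedes vaccination, so the visit name is a slip and no other baseline value could be used. The Cox paragraph is headed by baseline status, lists no group term and speaks of risk factors, so it may describe prognosis more than the vaccine effect. Section 6.1.3 also does not say outright that VE is taken from the adjusted model. All of this stands, and it limits the point to an inaccurate label, one differing age cut, one wrong visit and one unstated coding.

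A reader might infer three stronger things that the documents do not support:

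- **That exacerbation history conflicts with the randomisation.** It does not. Protocol section 6.6.3 says a total number is entered in SBIR, which fits the SAP's wording, and the label itself points to the two levels.
- **That the intended count is certain.** The Visit 1 total is the likely meaning. However, the SAP refers to the time before enrolment, eligibility counts the 12 months before Screening, and the SBIR count covers the year before Visit 1 and includes self-reported events. Which is meant remains an inference.
- **That VE could be materially distorted.** In the simulation the 95th percentile of the shift reached 28 points only when history was fitted as a number, which the SAP does not clearly prescribe, and only under assumed inputs.

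**Conclusion.** The point holds as a consistency defect with a small effect. Section 6.1.3 attributes to the randomisation an age cut and a country factor that the randomisation did not use. It names a spirometry that is not scheduled, and it leaves the history coding open. The first three can be read directly from the documents. The last is under-specification.

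Its weight is low. The AECOPD endpoints are tertiary (Protocol 11.3), comparisons between groups are descriptive (Protocol 11.13), and no confirmatory conclusion depends on these models. The number of subjects whose age level changes runs from none at a median of 59 to 52-60 of 140 at a median of 68. That range rests on assumed normal ages with SD 7 to 9. No material gain or loss of precision is expected either way. A claim that the vaccine estimate would be biased, or that adjusting for country is an error, would go beyond the documents.

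**What to change.** In both models of SAP section 6.1.3, use the categories already written in section 6.1.2:

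- age 40-59 or 60-80 years;
- moderate and severe AECOPD in the year before Dose 1, <2 or ≥2, from the Visit 1 total entered in SBIR;
- GOLD 2 or 3, as the grade entered in SBIR, which rests on the Screening spirometry.

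Using the SBIR entry for GOLD, and not a later re-derivation, keeps the model factor identical to the one minimised on. Keep country as an additional covariate outside the randomisation label, and remove the reference to a Visit 1 spirometry.

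The cost is a change of SAP wording. All the values are already collected, and nothing changes in the conduct of the trial.
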